1. PROTOCOL SUMMARY

Study Summary: HIV antiretroviral therapy has the potential to dramatically decrease HIV transmission worldwide¹; yet, a barrier to ending the AIDS epidemic in low-resource settings is the fact that healthcare is largely provided by traditional or spiritual healers rather than biomedical providers²⁻⁴, and there are no strategies in place to identify HIV-infected patients among Traditional Healer patients and link them to HIV care. In order to reach the UNAIDS 90-90-90 benchmarks HIV services must reach marginalized populations in endemic regions⁵, such as in southwestern Uganda. Uganda is one of seven sub-Saharan African countries accounting for 90% of all new HIV infections in this region⁶. HIV prevalence is 7.3%, with ~1.5 million people living with HIV/AIDS and 99,000 new infections in 2014⁷. However, only 50% of sexually active Ugandans have ever tested for HIV^{8,9}. Like much of sub-Saharan Africa, the majority of Ugandans utilize traditional and faith-based healers^{10,11}. Healers are more accessible than biomedical providers in resource-poor settings. Use is driven by preference as well as accessibility: healers are considered uniquely qualified to treat afflictions believed incurable by biomedicine¹². They are respected community leaders who shape clients' utilization of HIV services⁴. Those who utilize traditional healers may present to biomedical facilities late in their illness, or not at all¹³.

Study Aim and Overall Study Design: Develop a *POC HIV testing intervention at TH locations using* a cluster randomized study design. This study will be conducted among TH clients at 10 TH practice locations, to be compared with a control group receiving usual TH care. This pilot will offer HIV testing at TH practice sites to 250 TH clients. Primary outcome for this study will be *rates of HIV testing among TH clients*. Secondary outcomes will include i) *number of new HIV diagnoses among TH clients*, ii) *socio-demographic factors that predict HIV testing*, and iii) *percentage of patients with +HIV POC test who successfully link to HIV care in 3 months*.

This novel approach will have significant public health impact by expanding HIV testing and linkage to care, thereby reducing morbidity, mortality, and HIV transmission in a highly endemic region. This approach could be scaled for delivery in other HIV-endemic, medically pluralistic communities. Pilot results will be integrated with data from ongoing research in southwestern Uganda to propose a large-scale, cluster-randomized trial of this community-based HIV testing program in Eastern Africa.

Study Duration: 12 months (July 2019 – June 2020)

Primary Endpoint: Rate of HIV testing among TH clients at 3 months

Secondary Endpoints: i) number of new HIV diagnoses among TH clients at 3 months post enrollment; ii) percentage of patients with +HIV POC test who successfully link to HIV care at 3 months post enrollment and iii) variables that predict HIV testing.

2. BACKGROUND AND RATIONALE

HIV antiretroviral therapy (ART) has the potential to dramatically decrease HIV transmission worldwide^{1,2}. UNAIDS has set the goal that 90% of HIV-infected people should be tested and know their status, so they can access life-saving ART^{14,15}. In order to reach the UNAIDS benchmarks, HIV testing must reach marginalized populations in endemic regions¹⁶. Decentralized⁵, community-based^{4,5} approaches have been promoted as the key to expanding access to HIV care within low-resource settings. However, successful implementation of community-based services requires an understanding of the social and cultural context that influence community engagement with HIV services. Specifically, many HIV endemic regions are also *medically pluralistic* communities, where multiple explanatory frameworks for health and disease co-exist. In these areas, HIV testing and ART clinical care do not occur in isolation; traditional healers are commonly utilized instead of or concurrently with biomedical services^{8,9}. Therefore, the success of decentralized, community-based HIV services must be founded upon a thorough understanding of medical pluralism, and engagement with traditional healers as stakeholders in community health.

Uganda is one of seven sub-Saharan African countries accounting for 90% of all new HIV infections in this region¹⁷. HIV prevalence is 7.3%, with ~1.5 million people living with HIV/AIDS and 99,000 new infections in 2014⁶. However, only 50% of sexually active Ugandans have ever tested for HIV⁷. These data indicate poor progress towards the UNAIDS 90-90-90 targets for ending the HIV epidemic^{8,9}. *Our study will characterize factors that shape HIV testing behavior among communities with poor biomedical engagement and pilot an intervention to expand access to HIV testing.* Patients prefer to visit traditional healers to treat “African” diseases, believed incurable by biomedicine¹⁶. Healers in sub-Saharan Africa serve as herbalists, counselors, social workers, spiritual guides, and legal advisors¹². Pregnant women may prefer healers as home birth attendants over biomedical facility deliveries^{10,12,13,18-21}. Healers are authorities on health concerns, and considered more credible sources of health information than healthcare workers or biomedical clinicians^{18,20,21}. As higher rates of HIV testing^{3,11,13} and improved engagement with HIV care²² are correlated with regular contact with a health provider, healers are potential partners for HIV-infected clients throughout the care continuum²³⁻²⁵. *Our study will investigate feasibility of involving TH in HIV testing and pilot an intervention to expand HIV testing within communities that use traditional medicine.*

An AIDS-free generation cannot be achieved until HIV care is expanded to communities where the burden of disease continues undetected²⁶⁻²⁸. Healers have access to patients and potential influence to promote HIV testing and engagement with ART services. The proposed research holds promise for dramatically expanding HIV testing and early engagement with HIV services to a large population who otherwise may not access biomedical care.

3. STUDY DESIGN

3.1 Design: Previously conducted qualitative work and observational data will inform implementation of a pilot study, offering HIV testing at traditional healer locations in southwestern Uganda. No compensation will be provided for healers in the intervention or control arms of the intervention. We will follow Ugandan National protocols²⁹ to administer voluntary HIV counseling and testing at healer practices in Mbarara District. Clustering for this trial will occur at the level of healer practices. For the intervention arm, we will recruit 250 clients

from ten healer practice locations. For the control arm, we will observe 250 healer clients at ten healer locations undergoing “enhanced standard of care”, where healers will participate in a pre-trial educational session describing community HIV resources available for clients, and how to access them. Enrollment will take place from twenty traditional healer practices, over a period of four months. The follow up period will be three months. Primary outcome for this intervention *will be rates of HIV testing among TH clients (Figure).*

[figure not shown]

Figure. Approach for HIV testing pilot

select half to participate in the intervention arm (N=10); the remaining half will participate in the control arm (N=10). Healers in both study arms will keep a log of participants indicating whether HIV testing was delivered (intervention) or if the participant was referred to HIV testing (control). Many healers have little formal education and describe themselves as “illiterate”; study logbooks will be created accordingly. Research assistants will create stickers with de-identified study identification numbers for each participant. The healer will place the participant ID sticker in the log book (thereby avoiding the need to be able to write numbers); logs will show pictures for receiving point-of-care HIV testing, or not testing (in the intervention arm), or referral to the District HIV clinic for HIV testing, or not referring (for the control group). Healers will circle the corresponding picture for each participant based on the outcome of the session. Research assistants will be on site, or reachable via mobile phone, to answer any questions the healers have about record keeping or study procedures.

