4. RECRUITMENT AND ENROLLMENT

4.1 Inclusion and Exclusion Criteria: Inclusion criteria for healer clients are 1) 18 year of age or older; 2) able to provide informed consent, 3) not known to be HIV infected; 4) willing to be contacted for monthly follow up for 3 months; and 5) willing to complete an exit survey after 3 months. For the intervention (HIV testing) arm, participants must agree to receive their POC HIV test results. Exclusion criteria include being under the age of 18, incapable of giving informed consent, previously being diagnosed with HIV, being unwilling to receive HIV test results, and

unwilling to participate in the testing intervention. Participating healers are eligible to participate if they meet the UNAIDS definition of traditional healer⁸, and are willing to participate in study procedures. We will select from among healers with patient volume greater than 7 patients per week in order to ensure that participant recruitment progresses in a timely manner for this pilot study.

4.2 Informed Consent: We will obtain written informed consent from both traditional healers (N=20) and their clients (N=500) participating in this study. Participating clients must consent to providing three telephone contact numbers (self, friend, and family member), home address, and permission for the research team access to medical records from the District HIV clinic. In addition, they must consent to a home visit, if they are not reachable for follow up via phone. Healers must consent to keeping a logbook of which patients received HIV testing (intervention arm) or referred to HIV testing (control arm).

4.3 Subject Enrollment: One research assistant will be assigned to each arm of the study and will base themselves at healer practices to consecutively enroll 25 clients from each healer until we reach a sample size of N=500 (four-month enrollment period). The research assistant will assign a unique study ID number to each participant, collect demographic information, and locator information for the participant and two back up contacts. This information will be used for monthly follow-up assessments, and to deliver the exit interview.

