5. STUDY PROCEDURES

5.1 Intervention arm: Healers assigned to the intervention arm (N=10) will attend a half-day training session prior to trial initiation, led by District HIV clinic staff. This training session will demonstrate proper use and disposal of the point-of-care HIV testing kit and provide training regarding patient pre- and post-test counseling. Healers will be instructed to discuss the benefits of linking to HIV care, including importance of initiating treatment for HIV infection, reducing possible transmission to others, and health benefits of starting ART early, as part of post-test counseling. In addition, this training session will discuss resources available at the ISS clinic, including mental health counselors, family and partner support groups, counselors trained to discuss serostatus disclosure strategies, and reproductive health counselors. Supplies for point-of-care HIV testing and biohazard-compliant disposal will be provided to healers at the start of the trial. HIV 1/2 antibody point of care test (Oraquick[©]) will be administered to participants who agree to test. This test is non-invasive, conducted using oral fluids (rather than whole blood), and is FDA-approved for adult use, with results in 20 minutes. Test results are clearly marked with lines, rather than letters or numbers; this test is validated for use by non-medical personnel, with 99.9% specificity and 91.6% sensitivity. Clients with positive tests will be referred to the HIV clinic for Western Blot confirmation, and linkage to care. Following the healer visit, participants will be contacted once per month, for a period of 3 months, to assess for POC test results, and linkage to care for those who test HIV+.

5.2 Control arm: Control arm healers (N=10) will participate in a half-day session prior to trial initiation, led by District HIV clinic staff. This educational session will discuss WHO and Ministry of Health guidelines for HIV testing, who should receive HIV testing and how often, and where to receive it. Participating patients of healers will then receive “enhanced standard of care” as part of the control arm of the trial. Following the visit, study staff will contact the client once per month, for 3 months, to assess for HIV testing since enrollment in the study.

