assess if the partner meets criteria for inclusion as a participant; 2) if s/he meets inclusion criteria, the participant will undergo informed consent; and 3) we will conduct the remainder of the study procedures with both members of the couple present, and participating. If the partner does not meet criteria for inclusion, then the partner will be present for his/her partner's study procedures. If permission is refused, we will continue with pre-test counseling, testing, relaying of POC HIV test results, and post-test counseling in private. We will specifically train our research assistants to conduct post-test counseling that discusses issues specific to serodiscordant couples, including reducing risk of HIV transmission, reproductive issues and efficacy of PrEP. In addition, we will encourage the participant to disclose to his/her partner, and refer them to the HIV clinic, which has counselors who specifically assist clients with serostatus disclosure strategies and has resources for serodiscordant couples. By following a strict strategy of individual, private consent, our study procedures seek to reduce coercive influences from partners or family members who may be present with the participant.

MUST has completed numerous research studies on human subjects and maintained full confidentiality of participant records over the preceding decade. MUST has close collaborative relationships with the local HIV clinic, with no-cost resources for testing, treatment and counseling; participants will be referred to these resources as necessary over the course of this research. Due to the nature of this research, we will ensure that study staff undergo training on good clinical practices for human subjects research, with extensive piloting of informed consent and study practices, until staff are comfortable and knowledgeable. Specifically, we will train them to identify situations where coercion may be occurring as to avoid placing undue risk on the potential participant. Refresher courses on relevant topics will be carried out as needed, at least once every 6 months.

7.3 Data Safety and Monitoring: No stopping rules have been defined for this project, given the minimal risks to participants. The research procedures are minimally invasive and present low risks to the study participants. Subjects are volunteers and may drop out of the study at any time, without any recourse. They are informed of such during the consent process.

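### No section states that the POC HIV result is recorded at the visit, so the POC-positive count and the linkage denominator rest on later client report, which can undercount positives and may overstate linkage

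*Combined protocol and SAP*

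**What the plan says.** **Outcomes that need the result.** The Protocol Summary lists two HIV secondary endpoints at 3 months. One is the number of new HIV diagnoses among healer clients. The other is the "percentage of patients with +HIV POC test who successfully link to HIV care at 3 months post enrollment", whose denominator is by definition the POC-positive clients. Section 6.1 repeats both and names no data source for either.

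**What is written down at the visit.** Section 3.1 says of the log: "logs will show pictures for receiving point-of-care HIV testing, or not testing (in the intervention arm". Section 4.2 matches this: "Healers must consent to keeping a logbook of which patients received HIV testing (intervention arm) or referred to HIV testing (control arm". Neither mentions the result.

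**Where the result is collected.** Section 5.1 describes what happens once the client has left: "participants will be contacted once per month, for a period of 3 months, to assess for POC test results, and linkage to care". This is the only stated route for the POC result.

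**Other possible sources.**
- Clients consent in 4.2 to "permission for the research team access to medical records from the District HIV clinic". No section says these records define a diagnosis or linkage.
- Section 7.2, on couples, says: "We will specifically train our research assistants to conduct post-test counseling". Sections 5.1 and 8.1.2 give post-test counseling to the healers.
- Section 8.1.4 has research assistants working with intervention healers every few days to check testing procedure. It does not mention collecting results.

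**The concern.** The test reads out in about 20 minutes, so the result is known at the healer's practice on the day of enrolment. Nothing in the plan fixes it on paper at that point. It is instead asked about over the next three months, when the answer depends on the client being reached and being willing to report a reactive test. Section 8.1.2 itself describes the stigma, rejection and risk of partner violence that can follow a diagnosis.

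It is plausible that a client who conceals a reactive result or cannot be reached is also less likely to have gone to the clinic. Such a client would leave both the count of positives and the denominator for linkage. Clinic records would not bring that client back, because they show only people who attend: "Clients with positive tests will be referred to the HIV clinic for Western Blot confirmation, and linkage to care". Used alone, they fill the numerator of the linkage percentage and leave unlinked positives out of its denominator.

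Section 6.1 describes the results as central to showing feasibility for the follow-on grant. With about 20 positives expected, a few unrecorded results would change the reported linkage noticeably.

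**Working it through.** **Inputs from the documents.** 250 clients in the intervention arm, 90% uptake and 9% prevalence (4.4); sensitivity 91.6% and specificity 99.9% (5.1).

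**The plan's own figure.** 250 × 0.90 × 0.09 = 20.25, which matches the 20 or more new diagnoses stated in 4.4.

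**Reactive tests at the stated accuracy.** 225 tested × 0.09 × 0.916 = 18.5 true reactive; 225 × 0.91 × 0.001 = 0.2 false reactive; about 18.8 in all. The figures below use the plan's 20.25. The linkage percentages do not depend on that choice.

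**Assumptions (not in the documents).** True linkage among positives is L. Every linked positive becomes known, by report or clinic record. Unlinked positives become known with probability r, which covers both being reached and disclosing. Then:

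- observed count = 20.25 × [L + (1 − L)r]
- observed linkage = L / [L + (1 − L)r]

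| True linkage L | r | Observed count | Observed linkage | Overstatement (points) |
|---|---|---|---|---|
| 50% | 0.5 | 15.2 | 66.7% | 16.7 |
| 50% | 0.7 | 17.2 | 58.8% | 8.8 |
| 50% | 0.9 | 19.2 | 52.6% | 2.6 |
| 70% | 0.5 | 17.2 | 82.4% | 12.4 |
| 70% | 0.7 | 18.4 | 76.9% | 6.9 |
| 70% | 0.9 | 19.6 | 72.2% | 2.2 |
| 90% | 0.5 | 19.2 | 94.7% | 4.7 |
| 90% | 0.7 | 19.6 | 92.8% | 2.8 |
| 90% | 0.9 | 20.0 | 90.9% | 0.9 |

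Example, first row: 0.5 + 0.5 × 0.5 = 0.75; 20.25 × 0.75 = 15.2; 0.5 / 0.75 = 66.7%.

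**Case with no linkage bias.** If linked and unlinked positives become known with the same probability r, the count is 20.25 × r and observed linkage is Lr / r = L. At r = 0.7 the count is 14.2 and linkage is correct; at r = 0.5 and 0.9 the counts are 10.1 and 18.2. The count is then lower than in the table, but the linkage percentage is sound.

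**With the result recorded at the visit.** r = 1 for every tested client. The denominator is complete and this source of linkage bias disappears.

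**The case against.** **The plan does not say that nothing is recorded at the visit.** Section 4.3 bases research assistants at the practices, and 7.2 trains them in post-test counseling, so they may learn the result on the day. Section 7.5 mentions data collection documents without listing them. Section 3.1 relies on national testing protocols that are not reproduced, and its figure is not shown in the copy reviewed. A reader might infer that client self-report is established as the sole source. The documents do not go that far, and this part of the objection stands. It does not close the gap. Counseling is given to healers in 5.1 and 8.1.2, one assistant is assigned to each arm of ten practices (4.3), and 3.1 allows the assistant to be available only by phone. Even where an assistant hears the result, no section says it is recorded.

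**The bias is conditional.** A reader might infer that diagnoses will be biased down and linkage biased up. The second needs hidden or unreached positives to link less often, and the documents give no figure on this. A starker illustration is easy to build: with 18.5 reactive tests and 60% true linkage, hiding 20% of reactive clients, all unlinked, gives 14.8 positives and 0.60 / 0.80 = 75% linkage. But that means 0.20 / 0.40 = 50% of all unlinked clients are hidden while every linked one is known. It is an extreme case, not an expectation.

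**Follow-up is intensive.** Three phone contacts and consented home visits (4.2, 5.3) should limit loss. They do not address concealment.

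**These are secondary outcomes in an exploratory pilot.** That is true, and it limits how much weight the point carries.

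**Conclusion.** The concern holds in limited form. The log and the healer consent cover testing but not its result. The monthly contact is the only stated route for the result, and no section states a record made at the visit. As written, the POC-positive count and the linkage denominator rest on later client report. This can undercount positives. It overstates linkage only if hidden or unreached positives link less often.

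Under the assumed ranges (true linkage 50–90%; 50–90% of unlinked positives becoming known; all linked positives known), the expected 20.25 positives fall to about 15–20 and linkage is overstated by about 1–17 points. If non-disclosure is unrelated to linkage, only the count is affected. The documents do not show which case applies.

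The primary outcome, whether a client was tested, does not use the result and is unaffected. The gap should still be closed before the linkage percentage is used to plan the follow-on trial, because a result not recorded at the visit cannot be reliably recovered later.

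**What to change.** **Sections 3.1 and 5.1.** Record each POC result as reactive, non-reactive or invalid, against the study ID, at the visit. Either add result pictures beside the ID sticker in the log, or use a short research-assistant form completed at the visit or at the existing checks every few days. A form avoids relying only on a log kept by healers with little formal education.

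**Section 6.1.** Name the source for each HIV outcome:
- The visit record gives the count of POC-positives in the intervention arm and the linkage denominator.
- Monthly contacts and the already consented clinic records, used in the same way in both arms, give linkage, confirmation and diagnoses made elsewhere. The control arm has no POC test under the protocol, so the visit record cannot be the source for new diagnoses overall.
- Reactive results and confirmed diagnoses are reported separately, since positives are referred for confirmation.

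**Section 7.2 against 5.1 and 8.1.2.** State who gives post-test counseling, so that it is clear who holds the result.

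**Cost.** A few pictures or a one-line form, protocol wording, and healer consent wording in 4.2 extended to cover the result, with the ethics approval that this needs. Coded result pages would sit at the practice until collected and must be secured. They carry study IDs only, and under 5.1 the healer delivering the test and counseling already knows the result. The documents do not say whether the logbooks have been produced; if they have, the separate form is the simpler route.
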